7.6.10.3 Electrolytes

The following will be summarized by treatment group as worst CTC grade on-treatment per subject and as shift table of worst on-treatment CTC grade compared to baseline CTC grade per subject: sodium (high and low), potassium (high and low), calcium (high and low), magnesium (high and low), and Glucose Serum (fasting hyperglycemia and hypoglycemia regardless of fasting status).

The analyses will be conducted using the 30-day safety window.

A by-subject listing of these laboratory parameters will be provided.

7.6.10.4 Additional Analyses

In addition, further analyses on specific laboratory parameters will be performed by treatment group:

Abnormal Hepatic Function Test

The number of subjects with the following laboratory abnormalities from on-treatment evaluations will be summarized by treatment group:

- ALT or AST > 3 x ULN, > 5 x ULN, > 10 x ULN and > 20 x ULN
- Total bilirubin > 2 x ULN

- ALP > 1.5 x ULN
- Concurrent (within 1 day) ALT or AST > 3 x ULN and total bilirubin > 1.5 x ULN
- Concurrent (within 30 days) ALT or AST > 3 x ULN and total bilirubin > 1.5 x ULN
- Concurrent (within 1 day) ALT or AST > 3 x ULN and total bilirubin > 2 x ULN
- Concurrent (within 30 days) ALT or AST > 3 x ULN and total bilirubin > 2 x ULN

The analyses will be conducted using the 30-day safety window.

A by-subject listing of these specific abnormalities will be provided.

Abnormal Thyroid Function Test

The number of subjects with the following laboratory abnormalities from on-treatment evaluations will be summarized by treatment group:

- TSH value > ULN and
 - with baseline TSH value \leq ULN
 - with at least one FT3/FT4 test value < LLN within 2-week window after the abnormal TSH test
 - with all FT3/FT4 test values \geq LLN within 2-week window after the abnormal TSH test
 - with FT3/FT4 missing within 2-week window after the abnormal TSH test.
- TSH < LLN and
 - with baseline TSH value \geq LLN
 - with at least one FT3/FT4 test value > ULN within 2-week window after the abnormal TSH test
 - with all FT3/FT4 test values \leq ULN within 2-week window after the abnormal TSH test
 - with FT3/FT4 missing within 2-week window after the abnormal TSH test

The analyses will be conducted using the 30-day safety window.

A by-subject listing of these specific abnormalities will be provided.

7.6.11 Vital Signs and Pulse Oximetry

Vital signs and pulse oximetry (i.e. % oxygen saturation) collected on the CRF will be provided in separate listings.

7.6.12 Physical Measurements

Physical measurements will be listed by subject.

7.6.13 Non-Protocol Medical Procedures

Non-protocol medical procedures will be listed by subject.

[REDACTED]

[REDACTED]

[REDACTED]

[REDACTED]

- [REDACTED]
- [REDACTED]
 - [REDACTED]
 - [REDACTED]
 - [REDACTED]
 - [REDACTED]
 - [REDACTED]
- [REDACTED]

[REDACTED]

[REDACTED]

[REDACTED]

[REDACTED]

[REDACTED]

- [REDACTED]

7.6.15 Pregnancy

A by-subject listing of pregnancy tests results will be provided for randomized female subjects.

7.6.16 Adverse Events By Subgroup

Overall summary of any AEs and drug-related AEs by worst CTC grade (any grade, grade 3-4, grade 5) presented by SOC/PT and for each treatment group for the following subgroups:

- Sex (Male vs. Female)
- Race
- Age (< 65 vs. 65 - < 75 vs. 75 - < 85 vs. ≥ 85 vs. ≥ 75 vs. ≥ 65)
- Region (US/Canada/W.Europe/N.Europe vs. ROW)

These analyses will be conducted using the 30-day safety window only.

The table content is entirely redacted with black boxes, obscuring all data and headers.

- [REDACTED]
- [REDACTED]
- [REDACTED]
- [REDACTED]

- [REDACTED]
- [REDACTED]
- [REDACTED]
- [REDACTED]
- [REDACTED]
- [REDACTED]
- [REDACTED]
- [REDACTED]

8 CONVENTIONS

The following conventions may be used for imputing partial dates for analyses requiring dates:

- For missing and partial adverse event onset dates, imputation will be performed using the Adverse Event Domain Requirements Specification¹⁶
- For missing and partial adverse event resolution dates, imputation will be performed as follows (these conventions may change):
 - If only the day of the month is missing, the last day of the month will be used to replace the missing day. If the imputed date is after the death date or the last known alive date, then the latest known alive date or death date is considered as the resolution date.
 - If the day and month are missing or a date is completely missing, it will be considered as missing.

- Missing and partial non-study medication domain dates will be imputed using the derivation algorithm described in 4.1.3 of BMS Non-Study Medication Domain Requirements Specification¹⁷.
- Missing and partial radiotherapy and surgery dates will be imputed using algorithm described in [APPENDIX 2](#).
- For death dates, the following conventions will be used for imputing partial dates:
 - If only the day of the month is missing, the 1st of the month will be used to replace the missing day. The imputed date will be compared to the last known alive date and the maximum will be considered as the death date.
 - If the month or the year is missing, the death date will be imputed as the last known alive date.
 - If the date is completely missing but the reason for death is present, the death date will be imputed as the last known date alive.
- For date of progression after start of study therapy, the following conventions will be used for imputing partial dates:
 - If only the day of the month is missing, the 1st of the month will be used to replace the missing day. In case of the date of death is present and complete, the imputed progression date will be compared to the date of death. The minimum of the imputed progression date and date of death will be considered as the date of progression.
 - If the day and month are missing or a date is completely missing, it will be considered as missing.
- For date of progression to prior therapies, the following conventions will be used for imputing partial dates:
 - If only the day of the month is missing, the 1st of the month will be used to replace the missing day.
 - If the day and month are missing or a date is completely missing, it will be considered as missing.
- For other partial/missing dates, the following conventions were used:
 - If only the day of the month is missing, the 15th of the month will be used to replace the missing day.
 - If both the day and the month are missing, “July 1” will be used to replace the missing information.
 - If a date is completely missing, it will be considered as missing.

The following conversion factors will be used to convert days to months or years:

$$1 \text{ month} = 30.4375 \text{ days and } 1 \text{ year} = 365.25 \text{ days.}$$

Duration (e.g. time-to onset, time-to resolution) will be calculated as follows:

$$\text{Duration} = (\text{Last date} - \text{first date} + 1)$$

Last known alive date will be defined based on all appropriate dates collected on the CRF.

All statistical analyses will be carried out using SAS (Statistical Analysis System software, SAS Institute, North Carolina, USA) unless otherwise noted.

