8.2 Discontinuation from the Study

Participants who request to discontinue study treatment will remain in the study and must continue to be followed for protocol specified follow-up procedures. The only exception to this is when a participant specifically withdraws consent for any further contact with him/her or persons previously authorized by participant to provide this information.

- Participants should notify the investigator of the decision to withdraw consent from future follow-up **in writing**, whenever possible.
- The withdrawal of consent should be explained in detail in the medical records by the investigator, as to whether the withdrawal is from further treatment with study treatment only or also from study procedures and/or post treatment study follow-up, and entered on the appropriate CRF page.
- In the event that vital status (whether the participant is alive or dead) is being measured, publicly available information should be used to determine vital status only as appropriately directed in accordance with local law.
- If the participant withdraws consent for disclosure of future information, the sponsor may retain and continue to use any data collected before such a withdrawal of consent.

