4 ENDPOINTS

4.1 Primary Endpoints

Progression-free survival (PFS) is the primary endpoint. Two definitions are used for the analysis of PFS. The primary definition accounts for subsequent therapy by censoring at the last evaluable tumor assessment on or prior to the date of subsequent therapy. The secondary definition is irrespective of subsequent therapy and does not account for subsequent therapy.

Clinical deterioration in the absence of unequivocal evidence of progression (per RECIST v1.1 criteria) is not considered progression for purposes of determining PFS.

PFS rate at time T is defined as the probability that a subject has not progressed and is alive at time T following randomization. PFS rates at fixed time points (e.g. 6 months, depending on the minimum follow-up) are defined as the probability that a subject has not progressed and is alive at time T following randomization.

The first on-study tumor assessment is scheduled to be conducted at 12 weeks (± 1 week) following randomization. Subsequent tumor assessments are scheduled every 6 weeks (± 1 week) up to week 60, then every 12 weeks (± 2 weeks) until disease progression.

4.1.1 **Primary Definition of Progression-Free Survival (Accounting for Subsequent Therapy)**

The primary definition of PFS (PFS truncated at subsequent therapy, which includes anti-cancer therapy, tumor directed radiotherapy, or tumor directed surgery) is defined as the time between the date of randomization and the date of first documented tumor progression, based on BICR assessments (per RECIST v1.1 criteria), or death due to any cause, whichever occurs first.

Subjects who die without a reported progression will be considered to have progressed on the date of their death. The following censoring rules will be applied for the primary definition of PFS:

- Subjects who did not progress or die will be censored on the date of their last evaluable tumor assessment.
- Subjects who did not have any on study tumor assessments and did not die will be censored on their date of randomization.

- Subjects who receive subsequent anti-cancer therapy prior to documented progression will be censored at the date of the last evaluable tumor assessment conducted on or prior to the date of initiation of the subsequent anti-cancer therapy.

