4.2 Secondary Endpoints

4.2.1 Overall Survival

Overall survival (OS) is defined as the time from randomization to the date of death from any cause. For subjects that are alive, their survival time will be censored at the date of last contact date (or “last known alive date”). Overall survival will be censored at the date of randomization for subjects who were randomized but had no follow-up.

Follow-up visit #1 (FU1) should occur 30 days from the last dose and follow-up visit #2 (FU2) occurs approximately 100 days from last dose of study drug. After FU2, survival follow-up will be conducted every 3 months.

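### SAP section 8 discards a recorded year of death when the month is missing, so a death can be dated in an earlier calendar year than the record states

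*SAP*

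**What the plan says.** SAP section 8 (Conventions) gives three rules for incomplete death dates.

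- Only the day missing: the 1st of the recorded month is imputed, and then "The imputed date will be compared to the last known alive date and the maximum will be considered as the death date".
- Month or year missing: "If the month or the year is missing, the death date will be imputed as the last known alive date".
- Nothing recorded except a reason for death: "If the date is completely missing but the reason for death is present, the death date will be imputed as the last known date alive".

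The last known alive date comes from the case report form: "Last known alive date will be defined based on all appropriate dates collected on the CRF". Nothing ties it to the recorded year of death, and no other part of the supplied text sets a floor at that year.

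The death date defines OS (SAP 4.2.1): "Overall survival (OS) is defined as the time from randomization to the date of death from any cause". It also enters PFS (SAP 4.1.1): "Subjects who die without a reported progression will be considered to have progressed on the date of their death". Under the primary PFS definition this applies only if no new anti-cancer therapy was started first (SAP Table 4.1.1-1). SAP 7.6.1 tabulates deaths within 30 and 100 days of last dose.

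**The concern.** The first two rules treat recorded information differently. With the day missing, the recorded month and year limit how early the death can be placed. With the month missing, a recorded year counts for nothing, and the record is handled as if no date had been given. When the last contact was in a previous calendar year, the analysis dataset then holds a death date that the source record rules out.

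Such records could arise when a death is found after contact was lost. Protocol 8.2 says "publicly available information should be used to determine vital status only as appropriately directed in accordance with local law", and Protocol 8.3 has sites consult public sources and obtain the date of death by permissible local methods. In those cases the gap since last contact is longest. At stake are the event times for OS, the first endpoint tested after PFS, and for the PFS events that are deaths, as well as the classification of deaths by time since last dose.

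**Working it through.** The plan states no figure that rests on this rule, so there is none to reproduce. The check is date arithmetic, followed by an estimate of size.

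**1. The rule on single records.** Let L be the last known alive date and Y the recorded year of death, with the month missing. The SAP sets D = L. The earliest date that the record allows is D* = max(1 January Y, L). The error due to the rule is D* − D.

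| Last known alive | Death recorded as | SAP date | Earliest possible date | Error |
|---|---|---|---|---|
| 10 Nov 2018 | 2019 | 10 Nov 2018 | 1 Jan 2019 | 20 + 31 + 1 = 52 days |
| 15 May 2018 | 2020 | 15 May 2018 | 1 Jan 2020 | 365 + 231 = 596 days |
| 15 Oct 2018 | 2019 | 15 Oct 2018 | 1 Jan 2019 | 78 days |
| 20 Dec 2018 | 2019 | 20 Dec 2018 | 1 Jan 2019 | 12 days |
| 10 Feb 2019 | 2019 | 10 Feb 2019 | 10 Feb 2019 | 0 |
| 15 Oct 2018 | Jan 2019, day missing | 1 Jan 2019 | 1 Jan 2019 | 0 |

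The last row is the SAP's own day-missing rule. With the same last contact as the third row, it gives a date consistent with the record.

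**2. Death tables.** Take last dose 20 October 2018, last known alive 10 November 2018, death recorded as 2019. The SAP date is 21 days after last dose and enters the 30-day table. The earliest possible date, 1 January 2019, is 11 + 30 + 31 + 1 = 73 days after last dose and does not.

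**3. How often a year boundary is crossed.** Survival contact is every 3 months (SAP 4.2.1), with a 14-day window (Protocol 5.1). Assume the gap from last contact to death is uniform on 0–91 days, or on 0–105 days to allow for one window. The share of year-only deaths whose last contact was in the previous year is then about the mean gap divided by 365: 45.5/365 = 12.5%, or 52.5/365 = 14.4%. For these participants the error cannot exceed about 3 to 4 months (91 days, or 91 + 28 = 119 with both windows). It can be longer after loss of contact.

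**4. Effect on the OS hazard ratio.** The documents do not give the number of deaths without a month, so both settings below rest on assumptions.

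- *On-schedule contact.* 638 participants randomized 1:1, exponential survival with medians 33 and 47.1 months, analysis at 254 deaths, unstratified Cox model. Assume 1%, 5% or 10% of deaths lack a month and gaps are uniform on 0–91 or 0–119 days, with 60 runs per setting. On average about 0.5 to 3.5 deaths per trial were dated in the wrong year. The hazard ratio under the SAP rule differed from that under D* by less than 0.002 in every run.
- *Long gaps, all in one arm.* Same medians, 19-month accrual, cut-off at 40 months, with 3 or 5 deaths moved back by at least 6 months and 200 replicates per scenario. The mean shift was 0.003 to 0.007, and the most extreme 0.02. With the cases balanced between arms, the mean shift was about zero.

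**The case against.** The strongest reply is that this is a rare record type with almost no numerical effect. That stands. SAP 7.5 rounds efficacy estimates to two decimals, so a shift below 0.002 would rarely show. Nothing here indicates that a result would cross an OS critical value (0.673, 0.734 or 0.774). The protocol also limits the number of such records: survival contact every 3 months, sponsor-requested survival checks outside that schedule, and repeated documented attempts before a participant is declared lost.

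The PFS link is narrow as well. Under the primary definition only deaths without prior progression and without prior new anti-cancer therapy are affected. The supportive PFS analysis that censors after two missed assessments is a partial safeguard only, because it measures the gap to the imputed death date.

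It may also be said that the conventions are optional, since section 8 opens with "The following conventions may be used for imputing partial dates for analyses requiring dates". This does not hold: the death-date item has its own unconditional lead-in, and no alternative rule is given.

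Two stronger readings are tempting, and neither is supported.

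- A reader might charge the rule with the full distance to the end of the recorded year: 52 + 364 = 416 days in the first example, 596 + 365 = 961 in the second. Only 52 and 596 days are due to the rule. The rest is the ordinary cost of choosing the earliest possible date, which the SAP's day-missing rule also accepts.
- A reader might infer a bias between arms from the open-label design. The rule is the same in both arms, and the documents give no indication that year-only deaths would be more frequent in one of them.

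**Conclusion.** The rule is wrong as written: it can produce a death date that the recorded data exclude, and it is inconsistent with the SAP's own treatment of a missing day. It takes effect only when the month is missing, the year is recorded and the last known alive date lies in an earlier year. In any other case it agrees with the corrected rule.

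This is a minor specification flaw. The expected effect on the OS hazard ratio is below about 0.002 if 1% to 10% of deaths lack a month and contact runs to schedule. It reaches about 0.007 on average only under the unsupported assumption that 3 to 5 long-gap deaths all fall in one arm. The PFS effect was not simulated. A single record can be misplaced by weeks or longer, which matters for listings and for the 30- and 100-day death tables. It would go too far to infer that the primary or OS conclusion is at risk.

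**What to change.** Replace the month-or-year sentence for death dates in SAP section 8 with wording such as:

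> When the month of death is missing but the year is recorded, with or without the day, the death is dated to the later of 1 January of that year and the last known alive date. When the year is missing, the last known alive date is used.

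This extends the existing day-missing rule by one level and cannot contradict either the recorded year or the last contact. The phrase about the day is needed so that a record with day and year but no month still has a rule. The cost is one sentence in the SAP and one line of derivation code, best made before database lock. The residual drawback is small: deaths are still placed at the earliest possible date, as the day-missing rule already does.

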9 CONTENT OF REPORTS

All analyses described in this SAP will be included in the Clinical Study Report(s) except where otherwise noted. Refer to the Data Presentation Plan for mock-ups of all tables and listings.

10 DOCUMENT HISTORY

Table 10-1: Document History

Version Number		Description
1		Original issue
2		Employ hierarchical strategy to ORR after PFS and OS. [REDACTED]. Wording of cabozantinib dose delay and dose reductions are cleaned.

APPENDIX 1 TIME-TO ONSET AND TIME-TO RESOLUTION DEFINITION AND CONVENTIONS FOR SELECT ADVERSE EVENTS, IMMUNE-MEDIATED ADVERSE EVENTS AND EVENTS OF SPECIAL INTEREST

Time-to onset definition

Time-to onset of AE (any grade) for a specific category is defined as the time between the day of the first dose of study treatment and the onset date of the earliest AE (of any grade) in this category.

The time-to onset of AE (grade 3-5) for a specific category is defined similarly with an onset date corresponding to a grade 3-5 AE.

Time-to onset of drug-related AE (any grade or grade 3-5) for a specific category is defined similarly but restricted to drug-related AE.

Time-to onset for a specific subcategory is defined similarly but restricted to event of this subcategory.

Time-to resolution definition

In order to derive the time-to resolution, overlapping or contiguous AEs within a specific category or subcategory will be collapsed into what will be termed “clustered” AEs. For example, if a subject (without pre-treatment AE) experienced an AE from 1st to 5th January, another AE (with different PT but within same category) from 6th to 11th January and same AE from 10th to 12th January, these will be collapsed into one clustered AE from 1st to 12th January.

Key derivation steps for each type of clustered AEs is summarized as follows:

- For any grade AE: Collapse any on-treatment AE from the same category

- For drug-related any grade AE: Collapse any on-treatment drug-related AE from the same category
- For grade 3-5 AE: Collapse any on-treatment AE from the same category. Resolution will be based on the onset date of the earliest grade 3-5 records (if no grade 3-5 record, clustered AE is excluded)
- For drug-related grade 3-5 AE: Collapse any on-treatment drug-related AE from the same category. Resolution will be based on the onset date of the earliest grade 3-5 records (if no grade 3-5 record, clustered AE is excluded)

Time-to resolution of AE (any grade) for a specific category is defined as the longest time from onset to complete resolution or improvement to the grade at baseline among all clustered AEs experienced by the subject in this category per adverse event criteria category. Events which worsened into grade 5 events (death) or have a resolution date equal to the date of death are considered unresolved. If a clustered AE is considered as unresolved, the resolution date will be censored to the last known alive date. Improvement to the grade at baseline implies that all different events in the clustered adverse event should at least have improved to the corresponding (i.e. with same preferred term) baseline grade. This measure is defined only for subjects who experienced at least one AE in the specific category.

The time-to resolution of AE (grade 3-5) for a specific category is defined similarly with an onset date corresponding to a grade 3-5 AE.

Time-to resolution of drug-related AE (any grade or grade 3-5) for a specific category is defined similarly but restricted to drug-related AE.

The time-to resolution of AE (any grade or grade 3-5, drug-related or all) where immune modulating medication was initiated is defined similarly. For data presentation not restricted to IMAE, the additional condition that the subject started an immune modulating medication during the longest AE resolution period will be applied.

Time-to resolution for a specific subcategory is defined similarly but restricted to event of this subcategory.

The algorithm for collapsing adverse event records is using the following conventions:

For each subject and specified category, the corresponding adverse event records will be collapsed when:

- 1) Multiple adverse event records have the same onset date.
- 2) The onset date of an event record is either the same day or 1 day later than the resolution date of a preceding event record (contiguous events).
- 3) The onset date of an event record is after the onset date and prior to or on the resolution date of a preceding event record (overlapping events).

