7.5.6 Current Status of PFS and OS Follow-up

The extent of follow-up for survival, defined as the time between randomization date and last known alive date (for subjects who are alive) or death date (for subjects who died), will be summarized descriptively (median, min, max, etc.) in months for all randomized subjects.

The currentness of follow-up for survival, defined as the time between last OS contact (i.e., last known alive date or death date) and cutoff date (defined by last subject last visit date), will be summarized in months for all randomized subjects. Subjects who died and subjects with last known alive date on or after data cut-off date will have zero value for currentness of follow-up.

Minimum follow-up of OS for all randomized subjects, defined as the time from cutoff date to last subject's randomization date, will be summarized in months.

Time from last evaluable tumor assessment to cutoff date in months will be summarized by treatment group and overall for all randomized subjects. Subjects who have a PFS event will be considered as current for this analysis. The secondary definition of PFS will be used for this summary.

In addition, time to treatment discontinuation will be summarized and presented by treatment group using a Kaplan-Meier curve whereby the last dose date will be the event date for those subjects who are off study therapy. Median duration of study therapy and associated 95% CI will be provided. Subjects who are still on study therapy will be censored on their last dose date.

A by-subject listing will also be produced to accompany the subject time from last evaluable tumor assessment.

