7.6.6.3 Time-to Resolution of Select AE

Time-to resolution of the following specific events will be summarized separately for each category/subcategory.

- Time-to resolution of drug-related select AE (any grade, grade 3-5) by treatment group
- Time-to resolution of drug-related select AE (any grade, grade 3-5) where immune modulating medication was initiated, by treatment group

Time-to resolution analyses are restricted to treated subjects who experienced the specific events. Time-to resolution where immune modulating medication was initiated analyses are restricted to treated subjects who experienced the specific events and who received immune modulating medication during the longest select AE.

The analyses will be conducted using the 30-day safety window.

The following summary statistics will be reported: percentage of subjects with resolution of the longest select AE, median time-to resolution along with 95% CI (derived from Kaplan-Meier estimation) and ranges.

See time-to resolution definition subsection of [APPENDIX 1](#) for additional details.

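### A resolution date imputed and capped at death is then classed as unresolved, so an event reported to end in the month of death can be censored only because its day is missing

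*SAP*

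**What the plan says.** Two SAP rules act on the same date, one after the other.

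- **Section 8 (Conventions), missing and partial AE resolution dates.** "If only the day of the month is missing, the last day of the month will be used to replace the missing day". A cap follows: "If the imputed date is after the death date or the last known alive date, then the latest known alive date or death date" becomes the resolution date. The section does not say which of the two dates applies when a subject has died and they differ. It also describes the resolution-date rules as open to change.
- **Appendix 1, Time-to resolution definition.** Events that worsened to grade 5, or that "have a resolution date equal to the date of death are considered unresolved". Then: "If a clustered AE is considered as unresolved, the resolution date will be censored to the last known alive date". The rule does not separate reported dates from imputed ones.

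The outputs that use these dates are in section 7.6.6.3 for drug-related select AEs, which reports the "percentage of subjects with resolution of the longest select AE" and a Kaplan-Meier median, and in section 7.6.7 for time to resolution of immune-mediated AEs.

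**The concern.** The Appendix 1 rule has a sensible purpose. A site may close an ongoing event on the day the subject dies, and that should not count as recovery. But section 8 can itself place a resolution date on the death date. The site has then reported that the event ended in a given month, the SAP has created the coincidence with death, and Appendix 1 reads that coincidence as evidence of no resolution.

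The effect can spread beyond the single record. Appendix 1 needs every event in a cluster to have improved before the cluster counts as resolved, and it reports each subject's longest cluster. One reclassified record can make a whole cluster unresolved, and a later end date makes that cluster more likely to be the one reported. These summaries describe the reversibility of toxicity in the EU/ROW and US submissions.

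**Working it through.** The plan gives no figure to reproduce, so the check follows the rules through.

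**Step 1: the imputed date against the death date.** Let D be the death date, L the last known alive date and M the last day of the resolution month. Section 8 sets the imputed date to M. If the subject died in that month, M is on or after D.

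- If M is after D, the cap applies. With a death-date cap, the result is D.
- If M equals D, a death-date cap again gives D, and so does L = D, where no cap is triggered.

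So with a death-date cap the result is always D, and Appendix 1 classes the event as unresolved. With a cap at L, the result is D only if L = D.

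**Step 2: enumeration.** I took every death date in one illustrative year (2019) and every resolution date earlier in the same month, with the day treated as missing. A month of n days gives n(n − 1)/2 pairs: 7 × 465 + 4 × 435 + 1 × 378 = 3255 + 1740 + 378 = 5373. When L is several days before death, resolution dates after L are left out, so the denominator falls.

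| L relative to death | Unresolved, cap at death date | Unresolved, cap at L |
|---|---|---|
| Same day | 5373 of 5373 | 5373 of 5373 |
| 1 day before | 5373 of 5373 | 0 of 5373 |
| 5 days before | 4033 of 4033 | 0 of 4033 |
| 14 days before | 1720 of 1720 | 0 of 1720 |

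The cap is also triggered when M is after L. With a death-date cap, some resolutions in the month before death are therefore caught too: 0 of 11098 when L is the day of death or one day earlier, 1340 of 10978 at 5 days, and 3653 of 10006 at 14 days. With a cap at L, none is. These are counts of possible date combinations, not estimates of how often they occur.

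**Step 3: which cap does the SAP mean?** Section 8 says "then the latest known alive date or death date is considered as the resolution date". Section 7.5.6, in defining extent of follow-up, uses "last known alive date (for subjects who are alive) or death date (for subjects who died"). That pairing supports the death date for a subject who died. Section 8 also makes L and D coincide in some cases: a death date lacking month or year is set to L, and one lacking only the day is set to the later of L and the first of the month, which is L whenever L lies in that month. In those cases both readings give the same result.

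**Step 4: one event.** Onset 20 May; true resolution 5 June with the day not reported; death 25 June. Duration is last date − first date + 1 (section 8).

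- True duration: 16 + 1 = 17 days.
- Imputed date: 30 June, capped to 25 June, which equals the death date, so the event is unresolved.
- Censored at 36 + 1 = 37 days if L is 25 June, or at 31 + 1 = 32 days if L is 20 June.

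**Step 5: size.** If n subjects enter a category's summary and k of them have a reported cluster that changes status, percent resolved falls by 100k/n points. Neither document gives k or the frequency of partial resolution dates.

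**The case against.** The strongest objection is that the result depends on loose wording. Capped at a last known alive date even one day before death, no same-month record is reclassified. That stands, so the conclusion has to be conditional. It does not rescue the text: section 7.5.6 points the other way, the two dates sometimes coincide, and two programmers could derive opposite outcomes from the same sentence.

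Second, an end date known only to the month of death does not prove recovery before death; the event may have ended with the subject. Section 7.1.1 describes causality and action-taken fields, and I find no AE outcome field in either document. Calling such a case unresolved could be defended as a cautious choice, but the SAP does not present it as one. It follows from two rules written for other purposes.

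Third, the conventions are provisional, and Protocol follow-up of toxicities to resolution, with SAE updates due within 24 hours, should keep partial dates near death uncommon. Both points limit the importance. Neither removes the conflict.

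A reader might also infer that the sunitinib arm is hit harder, because the plan assumes a shorter median OS there (33 against 47.1 months). The documents do not support that. Overall mortality does not measure exposure to this rule. An affected record needs a drug-related select AE within the 30-day window, or an immune-mediated AE within the 100-day window, together with a partial resolution date, a death close to it and an effect on the longest cluster. Those AE categories are built around immunotherapy toxicity, so affected records could be as common or more common in Arm A.

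**Conclusion.** The conflict is real but conditional. With a death-date cap, or where the last known alive date equals the death date, every event reported with a resolution month and year in the month of death but no day is turned into a non-resolution by imputation alone. With a cap at an earlier last known alive date, it is not. The death-date reading is the more natural one.

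Within an arm, percent resolved can only fall or stay the same. The size cannot be computed and is probably small. No between-arm direction is established. PFS, OS, ORR and AE incidence are unaffected. A reader might conclude that the equality rule itself is wrong; it is reasonable for events ongoing at death, and the fault lies only in applying it to dates that section 8 created. This is a minor point, worth correcting because it costs little.

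**What to change.** 1. In section 8, state which date the cap uses for subjects who died.
2. In Appendix 1, apply the equal-to-death rule only to completely reported resolution dates or, if an AE outcome is collected, to events not recorded as resolved. An event with a reported resolution month whose date was imputed and capped then counts as resolved on the capped date.
3. Note with the tables that, with a death-date cap, such a duration is an upper bound. In the example, the event would count as resolved at 37 days although it truly lasted 17. The change restores the resolved status, not the exact duration.

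A count of affected records by arm would settle the size. The cost is one sentence in each of the two places, a table note and one condition in the derivation program, with no new data and no effect on any formal test.
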